4.2 Exploratory analysis of secondary endpoints

Adenoma frequency and other qualitative characteristics: H0: p1=p2 is tested against the alternative H1: $p1 \neq p2$.

The diagnostic performance of the proposed biomarker system of Neurotensin and IL-8, will be assessed against the current screening system with 2-weeks referral/FOB test by using propensity scoring in binary logistic regression.

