3.1 CONTROL(S) / COMPARATOR(S)

All individuals fulfilling the inclusion criteria will be enrolled. After the refinement of participants by the exclusion criteria blood sample will be drawn for Neurotensin and IL-8. Following the report of colonoscopy and the histology individuals will be assigned in three groups: a) group A - cancer patients, b) group B – adenoma (polyp) patients and c) group C – No pathology/normal colonoscopy. Two primary analyses will be conducted to define the cut-off plasma values for Neurotensin and IL-8 for a) diagnosing cancer (group A versus group C) and b) diagnosing adenomas (group B versus group C). A secondary analysis will be conducted comparing the performance of the Neurotensin/IL-8 system towards the 2-weeks referral and FOB test positive patients for the diagnosis of colorectal cancer and adenomas.

The reason for using participants without bowel pathology is because we need to define the "normal range" of Neurotensin and IL-8 serum values.

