3.5 PROPOSED SAMPLE SIZE / POWER CALCULATIONS

Assuming that the AUC of the new test is commensurate with the pilot study (AUC=0.85), we calculate the number of samples required to obtain a 95%

confidence interval of size 0.1. We assume that the ROC curve follows a binormal distribution, and that the prevalence of adenoma/cancer is between 20-30% in the study participants. We obtain that we require between 400 (30% prevalence) and 553 (20% prevalence) participants. We therefore target an enrollment of 500 patients. We intend to perform an interim analysis after 50% of the patients have been included and evaluated.

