4. STATISTICAL ANALYSIS

4.1 Confirmatory analysis of primary endpoints

In order to compare the low to high risk groups, the propensity score will be used that is the probability of a case being in a particular group based on a given set of covariates (e.g., age, gender, BMI and ethnic background). Generally, will be calculated using logistic regression with group (Treatment /Control) as dependent and covariates as independent variables. In order to deal with missing data in covariates, we will apply multiple imputation by either Separate creation of propensity scores from the matching or we will aggregate cases to get mean (median) propensity score. H0: p1=p2 is tested against the alternative H1: $p1 \neq p2$ using the exact Fisher tests.

A receiver operating characteristic (ROC) curve will be used to summarize the performance of the two-class classifiers (for Neurotensin and IL-8) for cancer and adenomas across the range of possible thresholds.

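### Section 4.2 assigns the comparison with 2-week referral/FOB to propensity-scored logistic regression, which on its ordinary readings does not test equal diagnostic performance

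*Protocol*

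**What the plan says.** Section 3.1 sets the aim, with both cancer and adenoma as targets: "A secondary analysis will be conducted comparing the performance of the Neurotensin/IL-8 system towards the 2-weeks referral and FOB test positive patients".

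Section 4.2, titled "Exploratory analysis of secondary endpoints", names the method: the marker system "will be assessed against the current screening system with 2-weeks referral/FOB test by using propensity scoring in binary logistic regression". It gives no dependent variable, tested coefficient, null hypothesis or significance level for this comparison. The one hypothesis written in 4.2 belongs to something else: "Adenoma frequency and other qualitative characteristics: H0: p1=p2 is tested against the alternative H1".

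Section 4.1 describes the propensity score. It "will be calculated using logistic regression with group (Treatment /Control) as dependent and covariates as independent variables", with age, gender, BMI and ethnic background as example covariates.

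**The concern.** The aim is comparative accuracy: judged against colonoscopy and histology, does the marker system do better than, as well as or worse than 2-week referral/FOB? The matching null is no difference in sensitivity and specificity (or in AUC) between the two tests.

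The coefficient of an ordinary binary logistic regression answers another question, namely whether a predictor is associated with the dependent variable. Two tests can both be strongly associated with disease and be equally good, or one can be clearly worse.

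The propensity score does not close the gap. It balances patient covariates between two groups of people. Where marker result, FOB or referral status and colonoscopy result all belong to one person, age, gender, BMI and ethnicity are the same for both tests and there are no two test groups to balance.

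This is the plan's only direct comparison with current practice. If a significant marker term were read as its answer, the report could describe performance relative to the current system without having estimated it.

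**Working it through.** **The plan's own figure.** Section 3.5 sizes the study on one AUC ("Assuming that the AUC of the new test is commensurate with the pilot study (AUC=0.85"), a 95% CI of width 0.1 and 20–30% prevalence. The binormal variance is V = 0.0099·exp(−A²/2)·[(5A²+8) + (A²+8)/k], with A = 1.414·z(0.85) = 1.4655 and k = (1−prevalence)/prevalence. Cases = 1.96²·V/0.05².
- 30%: V = 0.0781, cases = 120.0, N = 120.0/0.30 = 400.
- 20%: V = 0.0720, cases = 110.6, N = 110.6/0.20 = 553.

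Both stated figures reproduce. They concern the precision of a single AUC and do not bear on the 4.2 comparison.

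**Inputs for the check.** N = 500 (3.5: "We therefore target an enrollment of 500 patients"). Prevalence 20–30% (3.5). Pilot neurotensin sensitivity 77% and specificity 90% (2.1.1). Guaiac sensitivity 21.8–46.3% (1.8). Assumed, because the protocol does not give them: FOB specificity 90%, FOB status recorded and varying in all 500, and a two-sided 5% level.

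**Closed form at 25% prevalence (125 diseased, 375 not).** For a test with sensitivity Se and specificity 0.90, OR = Se/(1−Se) × 0.90/0.10. The variance of log OR is the sum of the reciprocals of the four expected cell counts, z = log OR/SE, and the chance of significance is Φ(z − 1.96).

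| Se | Cells | OR | log OR | SE | z | Chance |
|---|---|---|---|---|---|---|
| 0.77 | 96.25, 28.75, 37.5, 337.5 | 30.1 | 3.406 | 0.273 | 12.45 | about 100% |
| 0.463 | 57.88, 67.12, 37.5, 337.5 | 7.76 | 2.049 | 0.249 | 8.24 | about 100% |
| 0.218 | 27.25, 97.75, 37.5, 337.5 | 2.51 | 0.920 | 0.277 | 3.32 | 91% |

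Nothing in this calculation refers to the accuracy of the other test.

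**Simulation with the two tests set equal.** Model (a) is disease on marker plus propensity score. Model (b) adds FOB status. Model (c) is marker result on FOB status plus propensity score.
- 77%/90%, prevalence 20% and 30%: the tested term is significant in 100% of trials in (a), (b) and (c).
- 46.3%/90%, prevalence 25%: the marker term is significant in 100%.
- 21.8%/90%: 90% in (a) and (b) if the tests are independent given disease; 88% in (a) and 68% in (b) with conditional correlation 0.5.

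**Methods whose null is equal performance, at 77%/90%.** Exact McNemar rejects in 3.2–3.6% (sensitivity) and 3.6–4.0% (specificity). A stacked model of correct classification on test, with clustered errors, rejects in 5.3–6.9%. A Wald test of equal coefficients in (b) rejects in 4.8–5.2%.

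**Unequal tests.**
- Marker 60%/80% against 77%/90%: the marker term is significant and positive in 100% in (a). In (b) it is 100% if independent and 76% with correlation 0.5. The marker never had the larger odds ratio.
- Marker 40%/98.5% against 77%/90%: the odds ratios are (0.40/0.60)×(0.985/0.015) = 43.8 and 30.1. The marker had the larger odds ratio in 78% of trials, although its sensitivity is 37 points lower and its Youden index is 0.385 against 0.67.
- Uninformative marker (20%/80%): significant and positive in about 2.5%.

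**The case against.** **The null is not written.** Section 4.2 states no null, and detail for an exploratory analysis may sit in a SAP. A stacked model and an equal-coefficient test are both logistic regression and hold about 5%. This stands, so the criticism applies to the ordinary readings and not to every logistic model. The text points to neither alternative, though. In the stacked form a propensity score for test is constant and does nothing, and equal odds ratios are not equal sensitivity and specificity.

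**Near-100% rejection is power.** A reader might infer that the analysis has a false-positive rate near 100%. The documents do not support that. Rejecting an odds ratio of 1 for an informative marker is correct, and it becomes an error only if significance is reported as superiority, a rule that the protocol nowhere states.

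**Favouring a worse marker.** A reader might also infer that the method prefers a worse marker. A marker worse on both measures never had the larger odds ratio. Misranking appeared only where sensitivity was traded for specificity.

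**Paired data are assumed.** Section 3.1 words the comparator partly as a patient group, and section 3.2 mentions only positive FIT/FOB tests. Nothing says that FOB is recorded for everyone. This stands and limits the remedy. It does not rescue the method, because an odds ratio between referral groups is not a difference in accuracy either.

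**The stakes.** One might say that the case in section 1.8 for changing colonoscopy indications rests on this analysis alone. It does not: 1.8 ties that case to a connection between markers and disease, which the primary ROC analyses address, and 5.5 foresees a further multicentre study.

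**Conclusion.** The point holds as a mismatch between aim and method. Section 3.1 asks for a comparison of performance. Section 4.2 commits to a method whose ordinary coefficient tests an odds ratio of 1, with a propensity score that serves no purpose when both results come from one person. Since the marker term is significant in nearly every trial of two equally good tests at 46–77% sensitivity, and in 68–90% at 21.8%, its significance says nothing about better, equal or worse.

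These rates rest on N = 500, prevalence of 20–30%, an assumed specificity of 90%, a two-sided 5% level, and FOB status that is known and varies in all participants. Impact is limited: the analysis is exploratory, and neither the primary analyses nor the sample size depends on it. It should be corrected before the analysis is run.

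**What to change.** In 4.2, replace the propensity-scored logistic regression with a paired comparison in participants who have both a marker result and a recorded FOB/FIT result, and separately for 2-week referral yes/no.
- Report paired differences in sensitivity in group A and in group B, and in specificity in group C, with 95% CIs and exact McNemar tests and with the marker rule at a fixed cut-off.
- Report how many participants have each result, and how many are FOB-negative or not 2-week referrals.
- Where the comparator hardly varies because it was the reason for referral, state that comparative accuracy cannot be estimated and limit the conclusion to the marker's accuracy within that referred group.
- Report any logistic model separately, labelled as association or added value.

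The cost is a wording change, provided that FOB/FIT and referral status are recorded. The protocol does not confirm this, so it has to be checked first. The comparison will apply only to the referred cohort and will be imprecise for cancer alone: at the 4% pick-up rate in section 1.8, 500 participants would include about 500 × 0.04 = 20 cancers.

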4.3 Descriptive analysis

For qualitative characteristics we compute absolute, relative frequencies, and odds ratios. For quantitative variables we compute median, minimum and maximum, lower and upper quartile and graph them in box plots, mean and standard deviation are computed if appropriate.

Comparisons of quantitative variables between cases and controls using ttests or Mann-Whitney tests as appropriate.

4.4 Subgroup analyses

All analyses mentioned above are also performed stratified by gender, BMI and ethnic background respectively.

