3.3 OUTCOME MEASURES

The primary endpoints are firstly the cut-off of the serum Neurotensin and IL-8 values selected by the ROC curves and the demonstrated estimate of area under ROC curve (accuracy) in predicting colorectal cancer and colorectal adenomas.

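### Section 4.4 repeats every analysis, the confirmatory one included, within gender, BMI and ethnic strata, with no test of difference between strata and no exploratory label

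*Protocol*

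**What the plan says.** Section 4.4 of the protocol is one sentence: "All analyses mentioned above are also performed stratified by gender, BMI and ethnic background respectively".

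What stands above it in Section 4:

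- "4.1 Confirmatory analysis of primary endpoints": a two-sided comparison of proportions "using the exact Fisher tests", and ROC curves for each marker, for cancer and for adenoma.
- "4.2 Exploratory analysis of secondary endpoints": a comparison of adenoma frequency and other qualitative characteristics, and a comparison with the current referral and stool-test pathway.
- Section 4.3, headed descriptive: "Comparisons of quantitative variables between cases and controls using ttests or Mann-Whitney tests as appropriate".

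Section 3.1 sets two contrasts, cancer versus normal and adenoma versus normal: "Two primary analyses will be conducted to define the cut-off plasma values for Neurotensin and IL-8". Section 3.3 adds: "The primary endpoints are firstly the cut-off of the serum Neurotensin and IL-8 values selected by the ROC curves", together with the area under the curve.

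The protocol states no significance level, BMI categories or number of ethnic groups. Its only error-rate figure is the 95% confidence interval of size 0.1 in Section 3.5.

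**The concern.** The authors chose a status for each of the three preceding subsections (confirmatory, exploratory, descriptive) and gave Section 4.4 none. What 4.4 does fix is the method: repeat everything inside each stratum. That method answers whether the marker separates cases from controls in women, and separately in men. It does not answer whether the marker performs differently in the two. A significant result in one stratum beside a non-significant result in another is expected by chance when strata are small and the true effect is the same in both.

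At stake are statements that a marker works in only one gender or BMI group, and cut-offs set separately by stratum, resting on very few cancers.

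**Working it through.** **Inputs from the protocol.** N = 500, AUC 0.85, prevalence of adenoma and cancer combined 20–30%, total interval width 0.1 (Section 3.5); two markers and two contrasts (Sections 3.1 and 4.1); cancer pick-up rate 4% (Section 1.8).

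**Assumptions.** Two-sided alpha 0.05. The general 4% rate applies to this cohort: 0.04 × 500 = 20 cancers. Combined prevalence 25%, the midpoint, leaves 375 normal colonoscopies. Genders are equal in size: 10 cancers and about 188 controls each. Strata: 2 gender, 2 or 3 BMI and 2 ethnic (90/10), so 6 or 7 in all.

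**The plan's own figure.** The binormal variance is V = 0.0099·exp(−a²/2)·[(5a² + 8) + (a² + 8)/k], with a = 1.414·z(0.85) = 1.4655 and k = (1 − prevalence)/prevalence. The number of cases is 1.96²·V/0.05².

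- 20%: k = 4, V = 0.0720, 110.6 cases, N = 110.6/0.20 = 553.
- 30%: k = 2.33, V = 0.0781, 120.0 cases, N = 120.0/0.30 = 400.

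Both match Section 3.5. The sizing is for the whole cohort with cancer and adenoma pooled. No stratum was sized.

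**1. Same true AUC in both genders.** If each gender's test has power π, the chance that exactly one is significant is 2π(1 − π). Power was simulated for a two-sided Mann-Whitney test with 10 cancers and 188 controls, normal markers.

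| True AUC in both | π | 2π(1 − π) |
|---|---|---|
| 0.65 | 0.36 | 0.46 |
| 0.70 | 0.59 | 0.48 |
| 0.75 | 0.81 | 0.31 |
| 0.85 | 0.99 | 0.02 |

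Counting discordant pairs directly, across repeated simulations, gives about 30–50% for AUC 0.65–0.75 and 2% for 0.85. There is no true difference between genders in any row.

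**2. Neither marker works (global null).** The count is 6 or 7 strata × 2 markers × 2 contrasts = 24 or 28 tests. If they were independent, 1 − 0.95²⁴ = 71% and 1 − 0.95²⁸ = 76%. The strata overlap, so this was simulated (500 participants; 5% cancer, 20% adenoma, 75% normal; 1,500 runs):

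- Mann-Whitney: 56–65%.
- Fisher's exact test at a fixed marker threshold: 49% (6 strata) to 55% (7 strata).
- One Fisher test per stratum, one marker, one contrast, 7 strata: 21%.

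**3. Precision for cancer at AUC 0.85.** The Hanley-McNeil variance is [A(1 − A) + (n₁ − 1)(Q₁ − A²) + (n₀ − 1)(Q₂ − A²)]/(n₁n₀), with Q₁ = A/(2 − A) = 0.739 and Q₂ = 2A²/(1 + A) = 0.781. Width = 2 × 1.96 × SE.

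| Set | Cancers / controls | SE | Width |
|---|---|---|---|
| Whole cohort | 20 / 375 | 0.0546 | 0.21 |
| One gender | 10 / 188 | 0.0773 | 0.30 |
| One BMI third | 7 / 125 | 0.0925 | 0.36 |

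A 10% ethnic stratum would hold about 2 cancers. The symmetric interval then passes an AUC of 1, so no width is quoted for it.

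**The case against.** **The error rate is not in the document.** This stands. No alpha and no number of strata are stated. A reader might infer that testing is at full alpha and that a false subgroup finding is more likely than not. That needs a global null, alpha 0.05, and both markers and both contrasts counted. With independent tests at least 14 are needed to pass 50% (1 − 0.95¹⁴ = 51%), and one Fisher test per stratum gives about 21%.

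**If the markers perform as assumed, a significant stratum is a true positive.** This also stands. A reader might infer that most stratum findings would be chance, but the document does not support that: at AUC 0.85 the discordance in step 1 is 2%. The 0.85 comes, however, from a pilot with 13 colorectal cancer patients and 15 healthy controls (Section 2.1.1), so lower values need to be considered.

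**Section 4.4 does not claim equal standing.** Correct. It has its own heading, Section 2 calls the study a pilot, Section 5.5 foresees a multicentre study if results are promising, and Section 3 rules out effects on participants' care. What can be said is that 4.4 repeats a confirmatory analysis without giving the repeats a status.

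**Stratum cut-offs are an inference.** Partly right. Cut-offs are defined in Sections 3.1 and 3.3, and Section 4.1 only summarises ROC performance across thresholds. Whether 4.4 reaches back that far is arguable. Since the ROC curves in 4.1 are the tool by which the primary cut-offs are chosen, repeating them by stratum invites stratum cut-offs, and nothing excludes them.

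**Labels and alpha rules belong in a statistical analysis plan.** True of an omission alone. Here the protocol fixes the within-stratum method, and that method is the weakness.

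**Missing the 0.1 width is not caused by 4.4.** Correct: at 20 cancers the whole cohort already has a width of 0.21. Stratifying widens this to 0.30 or more.

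**Conclusion.** The point holds as a weakness of method and labelling in Section 4.4. Separate within-stratum tests cannot show a difference between strata, and nothing else is planned to do so. With about 10 cancers per gender and alpha 0.05, both assumed, a misleading contrast between genders arises in about 30–50% of trials at a common AUC of 0.65–0.75 and about 2% at 0.85. Under a global null with 24–28 assumed tests, the chance of at least one false rejection is roughly 50–65%, or about 21% on the narrowest count. Cancer AUC intervals about 0.30 wide per gender, and wider by BMI third, make stratum cancer cut-offs unreliable.

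The analysis of the whole cohort is not affected. This is a cheap improvement that should be made, not a fault that undermines the study.

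**What to change.** Replace the sentence in Section 4.4 with wording such as:

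> Subgroup analyses are exploratory. For each marker and each contrast, heterogeneity by gender, BMI (continuous) and ethnic background is assessed by a marker-by-factor interaction term in a logistic model for case status. AUCs within strata are shown with 95% confidence intervals only. No p-values, cut-offs or claims are derived within strata. Interaction p-values are read as exploratory, or are adjusted by Holm's method.

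The last sentence of that wording is needed. Three factors × two markers × two contrasts make 12 interaction tests, and 1 − 0.95¹² = 46% if they are uncorrected and treated as independent. With about 20 cancers these tests will also have limited power, so a non-significant interaction should not be reported as proof that strata are alike.

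The change needs no extra participants, samples or assays. The sponsor gives up significance claims and cut-offs specific to a stratum.

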4.5 Interim analysis

An interim analysis with regard to the primary endpoint will be performed after inclusion and evaluation of 250 persons. If H0 can be rejected at this stage the study will be stopped. All persons included in the study up to the decision to stop will be evaluated and considered for a secondary analysis. If H0 cannot be rejected at this stage, a re-design is possible because of the adaptive strategy.

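### The study is sized for the precision of an AUC, but the interim rule ends it at 250 on a significance test that would almost surely reject under the planning AUC

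*Protocol*

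**What the plan says.** Section 3.5 of the protocol gives the only justification of the sample size. It begins "Assuming that the AUC of the new test is commensurate with the pilot study (AUC=0.85" and seeks a 95% "confidence interval of size 0.1", under a binormal ROC curve and a prevalence of adenoma or cancer of 20-30%. The result is 400 participants at 30% and 553 at 20%, with 500 as target. The paragraph has no null hypothesis, significance level or power. It ends: "We intend to perform an interim analysis after 50% of the patients have been included and evaluated".

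Section 3.3 matches that estimation aim: "The primary endpoints are firstly the cut-off of the serum Neurotensin and IL-8 values selected by the ROC curves", together with the estimated area under the curve for cancer and for adenomas. Section 3.1 plans two primary analyses, cancer versus normal and adenoma versus normal.

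Section 4.5 sets the look at 250 persons, concerning the primary endpoint, and rules: "If H0 can be rejected at this stage the study will be stopped". Otherwise, "a re-design is possible because of the adaptive strategy". It states no level or boundary and does not say which hypothesis is meant. The only H0 in the protocol is p1=p2 (sections 4.1 and 4.2; Fisher's exact test is named in 4.1), and p1 and p2 are not defined.

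**The concern.** Sections 3.5 and 4.5 pursue different aims. Showing that a marker discriminates at all takes far fewer patients than estimating its AUC to within 0.05 either way. If the markers perform as the plan assumes, a stop triggered by a significant test will therefore fire at half the planned size, before the stated precision is reached. The better the markers work, the more surely the study ends without what it was sized to deliver. The cut-offs and AUCs, which are the product of this study, would then rest on half the cases. The stop cannot readily be undone once recruitment has closed.

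**Working it through.** **Inputs.** AUC 0.85, 95% interval of full width 0.10, binormal ROC, prevalence 20-30%, N of 400 and 553, target 500 (section 3.5); look at 250 (section 4.5); pilot neurotensin sensitivity 77% and specificity 90% (section 2.1.1); colonoscopy pick-up for cancer 4% (section 1.8, a background remark). Assumed, because the protocol states neither: a null AUC of 0.5 and a two-sided 0.05 level.

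**1. The plan's own figure.** The Obuchowski binormal variance, with k the ratio of controls to cases, is

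V = 0.0099 · exp(−A²/2) · [(5A² + 8) + (A² + 8)/k], with A = 1.414 · z(AUC).

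For AUC 0.85, A = 1.4655, A² = 2.1477 and exp(−A²/2) = 0.3417.
- Prevalence 20%, k = 4: V = 0.0720. Cases = 1.96² · V / 0.05² = 110.6, so N = 110.6 / 0.20 = 552.9.
- Prevalence 30%, k = 7/3: V = 0.0781. Cases = 120.0, so N = 120.0 / 0.30 = 400.0.

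The stated 553 and 400 are reproduced. The same formula therefore serves for the look.

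**2. Interval width if the study stops at 250.** Width = 3.92 · √(V / cases).

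| Prevalence | Cases at 250 | Width at 250 | Cases at 500 | Width at 500 |
|---|---|---|---|---|
| 20% | 50 | 0.149 | 100 | 0.105 |
| 30% | 75 | 0.126 | 150 | 0.089 |

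At 250 the interval is 26% to 49% wider than the 0.10 planned. These figures pool adenoma and cancer. Each primary contrast in section 3.1 has fewer cases and is less precise.

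**3. Chance that the rule fires.** Power = Φ((AUC − 0.5 − 1.96 · SE0) / SE1), with SE0² = (N + 1) / (12 · cases · controls) and SE1 = √(V / cases).
- 50 vs 200: SE0 = 0.0457, SE1 = 0.0379, giving Φ(6.86), over 99.9%.
- 75 vs 175: SE0 = 0.0399, SE1 = 0.0323, giving Φ(8.42), over 99.9%.
- Cancer alone, if yield is 4% (10 vs 240): SE0 = 0.0934, SE1 = 0.0805, giving Φ(2.07), about 98%.

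If the true pooled AUC is lower, the chance at 250 (Hanley-McNeil variance for SE1) is 91-97% at AUC 0.65 and 59-71% at AUC 0.60.

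**4. The other reading of H0.** If p1 and p2 are the proportions testing positive, the pilot's neurotensin figures give 77% versus 100% − 90% = 10%. With 10 cancers against 190 controls, Fisher's exact test at 0.05 has 99.8% power. Both readings give the same answer.

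**5. Type I error, only if 0.05 is used at both looks.** Test statistics at half and full information have correlation √0.5. The chance that either exceeds 1.96 in absolute value is 0.083. A constant critical value of about 2.178 would restore 0.05.

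**6. Would an adjusted level repair the rule?** With 2.178 in place of 1.96, step 3 gives Φ(6.60) and Φ(8.15) for the pooled comparison, still over 99.9%, and Φ(1.82), about 97%, for 10 cancers. Adjusting the level leaves the conflict with section 3.5 in place.

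**The case against.** The strongest objection is that H0 is not defined, so the stopping probability rests on a null that the reviewer supplied. That stands as a limit. A null set at some minimum acceptable AUC would be rejected less often. The protocol states none, however, and its one written hypothesis, p1=p2, leads to the same result.

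Almost certain stopping also depends on an AUC of 0.85, which comes from the pilot's neurotensin result for cancer. No adenoma AUC is given, and section 4.5 does not say whether one or all of the marker and disease comparisons must reject. This too stands: at a true AUC of 0.60 the stop is only somewhat more likely than not. But 0.85 is the plan's own assumption, and a rule that defeats the design when that assumption is true is a flaw in the rule.

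Three stronger readings are tempting and are not supported:
- *The plan inflates type I error.* No level is stated for either look, and a statistical analysis plan that is not shown may set one and may describe the adaptive strategy. The 8.3% is conditional on 0.05 twice. Nor does it follow that later p-values cannot be interpreted.
- *The interim causes the poor precision for cancer.* With 10 cancers the width is about 0.32, but at the same 4% yield the full 500 gives 20 cancers and a width of about 0.22. Most of the shortfall from 0.10 would exist without any look, and the 0.10 target was computed for the pooled prevalence.
- *The plan yields about 10 cancers at 250.* The 4% is a background remark, not a planning figure for this cohort. Section 3.2 also lists symptoms and positive stool tests, so the yield may differ.

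It may finally be said that section 2 calls this a pilot, that results do not affect participants' care, and that section 5.5 foresees a multicentre study. That limits the harm, but the document still contradicts itself on what the study must achieve before it ends.

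**Conclusion.** The point holds as a contradiction in what the protocol states, not as a detail left to a later document. Section 3.5 requires at least 400 participants for the planned precision, and section 4.5 ends the study at 250 on a criterion that the sizing never uses. Under the planning AUC, a null of 0.5 and a two-sided 0.05 level, the stop has over 99.9% probability for pooled neoplasia. The direct loss is a pooled interval width of 0.126-0.149 instead of 0.089-0.105, with the two separate primary contrasts less precise still. The 98% for cancer alone depends further on the 4% yield. The type I error figure of about 8.3% is secondary and conditional.

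**What to change.** In section 4.5, delete the sentence that stops the study when H0 is rejected. If the sponsor wants to keep an early stop, allow it only when the planned interval width of 0.1 has been reached for each primary contrast. Use the look at 250 to check case yield, haemolysis and other sample failures, assay failures and recruitment. Limit any re-design to resizing on the observed prevalence, without looking at marker results by outcome. Run the primary ROC analysis once, at the planned 500. If a significance test is kept anywhere, define its H0 and level.

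The cost is protocol wording and the loss of a possible finish about six months early (half of the 12 months in section 1.6).
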